3.4.3 Pharmacodynamic and Biomarker Parameters

3.4.3.1 Assessment of Immune Dysfunction

The diagnostic immunological profiling tool is based on novel, standardized techniques revealing in-depth information on immune phenotype and -function, allowing for standardized and robust data readout and ensuing technology transfer. These assessments are based on a collaboration with [name], PhD, Rigshospitalet and the Persimune.org project.

These investigations will be performed at a few central laboratories to assure quality and interlaboratory reproducibility. In combination with MRD results and assessment of subclonal development, immune phenotyping data may indicate optimal treatment length (6 months or 3 months).

- Immune phenotyping: A 10-color flow cytometry whole blood panel comprising 10 different tests has been custom-designed (DuraClone, Beckman Coulter) and is currently under validation at the Dept. of Clinical Immunology, Rigshospitalet. The ten different flow tests (I-X) evaluates: I) Major cell lineages in the blood (proportions and counts), II) B cell subsets, III) T cell subsets, IV) T cell receptor (TCR) subsets, V) Regulatory (Treg) and Th17 cells, VI)

 Dendritic cells, VII) Myeloid cells, VIII) Erythrocytes as surrogates for asplenism, IX) Platelets and platelet-leukocyte co-aggregates and X) Neutrophil phagocyte function. The panel captures multiple patterns predictive for cancer patients i.e. deviated maturation, acute/chronic activation, exhaustion, migration/trafficking and expression of immune checkpoint markers (PD-1, PD-1L, CTLA-4, FoxP3, Helios, CD25, TLR2, TLR4, CD38) which will also be extended with assessment of NK cell function and subtypes as well as additional immune activation markers.¹⁻⁸
- Immune function: Stimulated immune response & platelet function are assessed by TruCulture® (Myriad RBM), which assesses the induced innate and adaptive immune responses to whole blood ligand stimulation. Five different stimuli I-V are applied to screen the response to signaling pathways via Toll Like Receptors (TLRs), critical for the anticancer immune response as TLR ligands may break tolerance to self-antigens and promote immune responses to tumor antigens^{9,10}: I) Zymosan; II) Poly I:C; III) Resiguimod; IV) ODN + LPS and

V) NegCo. TruCulture® are currently validated at the Dept. of Clinical Immunology, Rigshospitalet and being tested for assessment of immune function in CLL at baseline and during treatment with targeted small molecules. TruCulture® provides an extensive data-readout, with cytokine response data available within days whereas Multiplate®/TEG® provides real-time results also on platelet function and complement cascades. Furthermore, transcriptomics by RNAseq assures in depth analyses of the molecular basis for immune changes upon treatment in stimulated and unstimulated cells.

3.4.3.2 MRD Assessment, Analysis of Subclonal Development

Minimal residual disease (MRD) levels will be examined by quantitative highly sensitive flow cytometry (MRD flow) in the peripheral blood and in the bone marrow at: The Department of Hematology, Rigshospitalet, Copenhagen University Hospital, MRD will be quantified by eight-color flow cytometry with a sensitivity of at least 10⁻⁴ or by DNA based methods.³⁵ MRD assessments of peripheral blood are to be performed at screening (for baseline characterization of the individual CLL clone), at 3 and 6 months after treatment initiation/start of observation, thereafter once a year for 3 years.

In addition, an NGS capture-based assay for MRD detection based on recurrent mutations and IGHV sequence is under development. DNA is prepared from patient samples at time of MRD assessment by flow cytometry. After full enrollment, these DNA samples will be analyzed by the NGS assay to allow for direct comparison of MRD assessment by the two methods and to allow for assessment of subclonal development during and after treatment. Furthermore, BH3 profiling as developed in collaboration with Assoc. [name], Dana Farber Cancer Institute, will be employed for assessment of sensitivity to various targeted therapies of viably frozen primary CLL cells from enrolled patients at baseline. The results of BH3 profiling will be correlated with long term outcome for the patients.

[figure not shown]
3.5 RATIONALE FOR STUDY DESIGN AND DOSING REGIMEN

Preclinical data supports the combination of BTK inhibitors and the bcl-2 inhibitor venetoclax. The combination of BTK inhibitors and venetoclax showed synergy in a diffuse large B cell lymphoma (DLBCL) cell line model ²⁸ and in primary CLL cells ³⁰ as well as in Mantle Cell Lymphoma (MCL) cell lines. ³⁶ Early clinical trials are currently testing the combination of venetoclax and acalabrutinib for clinical use, with no unexpected toxicities reported so far for combination of BTK and bcl-2 inhibitors through scientific meetings, publications or internal reports from the marketing holders. ³⁷ Translational data for patients treated with BTK inhibitors ^{6,25,26} and venetoclax ²⁷ indicate that immune function can be at least partly restored on treatment with decreasing incidence of infections over time on treatment and improved immune parameters. These translational data thus

support the hypothesis that short duration (3 months) treatment with the combination of acalabrutinib and venetoclax will improve the immune function for patients with newly diagnosed CLL at high risk of infection and/or treatment within 2 years.

Based on our collaboration with PERSIMUNE.org for multidimensional data-capture, genetic and functional analyses of primary CLL patient samples from our biobank covering samples from +700 patients since 2002 and machine-learning modelling in collaboration with DTU compute, we have developed a novel algorithm for identification of CLL patients at increased risk of infection prior to any CLL specific treatment and/or early CLL treatment, CLL-TIM (see figure 3-2). This model extends on known prognostic markers in CLL as defined based on the CLL-IPI criteria. 38,39 We are thus able to identify a subgroup of newly diagnosed CLL patients without IWCLL treatment indication, 40 who are at high risk of infection and/or treatment by the CLL-TIM. More than 65% of these patients will have a severe infection or CLL treatment within two years.

Figure 3-2. Performance of the CLL-TIM predicting high risk CLL patients for infection and/or treatment at time of diagnosis.

Agius et al, EHA 2018, Abstract PS-1103 and manuscript in preparation

In line with the START trial demonstrating that early treatment is superior to deferred treatment in HIV due to impact on multiple causes of death all related to immune dysfunction,⁴¹ we aim at improving the immune function by early treatment. Consequently, the aim of the current trial is to evaluate whether short-term, pre-emptive combination treatment with venetoclax + acalabrutinib in patients with high risk of infection and/or CLL treatment can change the natural history of immune function in CLL and diminish the need for cytotoxic chemotherapy.

3.6 SELECTION OF STUDY POPULATION

3.6.1 Inclusion Criteria

Eligible subjects will be considered for inclusion in this study if they meet all the following criteria:

- 1. CLL diagnosed according to IWCLL criteria within one year prior to randomization
- 2. High risk of infection and/or progressive treatment within 2 years according to CLL-TIM
- 3. IWCLL treatment indication not fulfilled
- 4. Life expectancy > 2 years
- 5. Age at least 18 years
- 6. Ability and willingness to provide written informed consent and adhere to study procedures and treatment
- 7. Adequate bone marrow function as indicated by platelets above 100 x 10E9, hemoglobin above 10 g/dL and neutrophils above 1 x 10E9
- 8. Creatinine clearance above 30 mL/min directly measured with 24hr urine collection or calculated according to the modified formula of Cockcroft and Gault
- 9. Adequate liver function as indicated by a total bilirubin≤ 2 x, AST or ALT ≤ 2.5 x the institutional ULN value, unless directly attributable to the patient's CLL or to Gilbert's Syndrome.
- 10. Negative serological testing for hepatitis B (HBsAg negative and anti-HBc negative; patients positive for anti-HBc may be included if PCR for HBV DNA is negative and HBV-DNA PCR is performed every month until 12 months after last treatment cycle), negative testing for hepatitis C RNA within 6 weeks prior to registration.
- 11. Eastern Cooperative Oncology Group Performance Status (ECOG) performance status 0-2.
- 12. Woman of childbearing potential (WOCBP) who are sexually active must use highly effective methods of contraception during treatment and for 30 days after the last dose of investigational drugs.
- 13. Willing and able to participate in all required evaluations and procedures in this study protocol including swallowing capsules without difficulty.
- 14. Ability to understand the purpose and risks of the study and provide signed and dated informed consent and authorization to use protected health information.

3.6.2 Exclusion Criteria

Subjects will be ineligible for this study if they meet any of the following criteria:

- 1. Prior CLL treatment (including monoclonal antibodies, chemotherapy, small molecules, including CD20 antibodies, BTK inhibitors and bcl-2 inhibitors for any indication)
- 2. Transformation of CLL (Richter's transformation)

- 3. Previous autoimmune disease as AIHA (autoimmune hemolytic anemia) or ITP (idiopathic thrombocytopenic purpura) treated with immune suppression or uncontrolled AIHA or ITP
- 4. History of progressive multifocal leukoencephalopathy
- 5. HIV infection (a negative test required)
- 6. Known active infection
- Malignancies other than CLL requiring systemic therapies (except anti-hormonal therapies) or considered to impact survival
- 8. Requirement of therapy with strong CYP3A4 and CYP3A5 inhibitors/inducers or anticoagulant therapy with vitamin K antagonists
- 9. History of bleeding disorders or current platelet inhibitors or anticoagulant therapy
- 10. History of clinically significant cardiovascular disease such as arrhythmias, congestive heart failure, or myocardial infarction within 6 months of screening, or any Class 3 or 4 cardiac disease as defined by the New York Heart Association Functional Classification, or corrected QT interval (QTc) > 480 msec at screening.
- 11. History of stroke or intracranial hemorrhage within 6 months prior to registration.
- 12. Use of investigational agents which might interfere with the study drug within 28 days prior to registration.
- 13. Vaccination with live vaccines within 28 days prior to registration.
- 14. Major surgery less than 30 days before start of treatment. Note: If a subject had major surgery, they must have recovered adequately from any toxicity and/or complications from the intervention before the first dose of study drug.
- 15. Known hypersensitivity to any active substance or to any of the excipients of one of the drugs used in the trial.
- 16. Pregnant women and nursing mothers (a negative pregnancy test is required for all women of childbearing potential within 7 days before start of treatment; further pregnancy testing will be performed regularly).
- 17. Fertile men or women of childbearing potential unless: surgically sterile or ≥ 2 years after the onset of menopause or willing to use two methods of reliable contraception including one highly effective contraceptive method (Pearl Index <1) and one additional effective (barrier) method during study treatment and for 30 days after the end of study treatment.
- 18. Legal incapacity.
- 19. Persons who are in dependence to the sponsor or an investigator
- 20. Persons not considered fit for the trial by the investigator
- 21. Malabsorption syndrome, disease significantly affecting gastrointestinal function, or resection of the stomach or small bowel that is likely to affect absorption, symptomatic inflammatory bowel

- disease, partial or complete bowel obstruction, or gastric restrictions and bariatric surgery, such as gastric bypass.
- 22. Prothrombin time/INR or aPTT (in the absence of Lupus anticoagulant) > 2x ULN.
- 23. Requires treatment with proton pump inhibitors (e.g., omeprazole, esomeprazole, lansoprazole, dexlansoprazole, rabeprazole, or pantoprazole). Subjects receiving proton pump inhibitors who switch to H2-receptor antagonists or antacids are eligible for enrollment to this study.

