3.11.2 Prohibited or Restricted Concomitant Therapy

Patients who require the use of any of the prohibited therapies listed below will be discontinued from study treatment.

Use of the following therapies is prohibited during the study:

- Cytotoxic chemotherapy
- Radiotherapy
- Immunotherapy
- Any therapies intended for the treatment of leukemia whether FDA-approved or experimental (outside of this study)
- Anti-retroviral medications
- Warfarin and other vitamin K antagonists.

Please note: Patients being treated with Direct anti-coagulants (DOACs), acetylsalicylic acid and non-steroid anti-inflammatory drugs (NSAIDs) can be included but must be properly informed about the potential risk of bleeding under treatment with acalabrutinib.

Live-virus vaccines should not be given within 28 days prior to the initiation of study treatment, at any time during study treatment, or following study treatment until B-cell levels have returned to normal and any neutropenia have resolved.

Use of the following concomitant medications is prohibited:

- Steroid therapy for anti-neoplastic intent, with the exception of inhaled steroids for asthma, topical steroids, steroids up to 25 mg of prednisolone daily to control autoimmune phenomenon's, or replacement/stress corticosteroids.
- Strong CYP3A inhibitors (see appendix 3 for examples).

Concomitant medications that fall into the categories below could potentially lead to adverse reaction(s) and should be considered cautionary (except where noted). If a potential study patient is taking any of the medications in the categories described below, the investigator will assess and document the use of medications known or suspected to fall in the following medication categories:

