3.12.2 Drug-Drug Interactions

At the systemic exposure levels expected in this study, acalabrutinib inhibition of CYP metabolism is not anticipated. However, acalabrutinib is metabolized by CYP3A. Concomitant administration with a strong CYP3A and P-glycoprotein (P-gp) inhibitor, itraconazole increased exposure by approximately 5-fold. Conversely, concomitant administration of with a strong CYP3A inducer, rifampin decreases acalabrutinib exposure and could reduce efficacy. Consequently, the concomitant use of strong inhibitors/inducers of CYP3A (see Appendix 3) should be avoided when possible.

Co-administration of 400 mg once daily ketoconazole, a strong CYP3A, P-gp and BCRP inhibitor, for 7 days in 11 previously treated patients with NHL increased venetoclax Cmax by 2.3-fold and AUC∞ by 6.4-fold. Co-administration of 50 mg once daily ritonavir, a strong CYP3A and P-gp

inhibitor, for 14 days in 6 healthy subjects increased venetoclax Cmax by 2.4-fold and AUC by 7.9-fold. Co-administration of venetoclax with other strong CYP3A4 inhibitors is predicted to increase venetoclax AUC by on average 5.8- to 7.8-fold.

Co-administration of a 600 mg single dose of rifampin, a P-gp inhibitor, in 11 healthy subjects increased venetoclax Cmax by 106% and AUC∞ by 78%. Concomitant use of venetoclax with P-gp and BCRP inhibitors at initiation and during the dose-titration phase should be avoided; if a P-gp and BCRP inhibitor must be used, patients should be monitored closely for signs of toxicities.

Co-administration of bile acid sequestrants with venetoclax is not recommended as this may reduce the absorption of venetoclax. If a bile acid sequestrant is to be co-administered with venetoclax, the SmPC for the bile acid sequestrant should be followed to reduce the risk for an interaction, and venetoclax should be administered at least 4-6 hours after the sequestrant.

If medically justified, subjects may be enrolled if such inhibitors or inducers can be discontinued or alternative drugs that do not affect these enzymes can be substituted within 7 days before first dose of study drug. If a subject requires a strong CYP3A4 while on study, the subject should be monitored closely for any potential toxicities.

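### Patients on a direct oral anticoagulant or acetylsalicylic acid are ineligible under exclusion 9 but includable under Section 3.11.2; the rule for strong CYP3A inhibitors also needs reconciling

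*Protocol*

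**What the plan says.** **Antithrombotic drugs.** Section 3.6.2 opens its list with "Subjects will be ineligible for this study if they meet any of the following criteria". Criterion 9 reads "History of bleeding disorders or current platelet inhibitors or anticoagulant therapy". It carries no exception, and the synopsis repeats it word for word. Criterion 8 separately excludes "Requirement of therapy with strong CYP3A4 and CYP3A5 inhibitors/inducers or anticoagulant therapy with vitamin K antagonists".

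Section 3.11.2 puts "Warfarin and other vitamin K antagonists" on its list of prohibited therapies. Directly below, a note says "Patients being treated with Direct anti-coagulants (DOACs), acetylsalicylic acid and non-steroid anti-inflammatory drugs (NSAIDs) can be included", on condition that they are informed of the bleeding risk with acalabrutinib.

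**Strong CYP3A inhibitors.** Section 3.11.2 lists them among prohibited concomitant medications and repeats the ban in its interaction table and closing sentence. Appendix 3 labels them prohibited. Section 3.11.2 also opens with a stopping rule: "Patients who require the use of any of the prohibited therapies listed below will be discontinued from study treatment". Section 3.12.2 is softer. It asks only that strong CYP3A inhibitors and inducers be avoided where feasible, and later adds: "If a subject requires a strong CYP3A4 while on study, the subject should be monitored closely for any potential toxicities".

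**The concern.** Eligibility has to give one answer per patient. Here, a site that works from the exclusion list rejects a patient on a DOAC or acetylsalicylic acid, and a site that works from the concomitant-therapy section enrols the same patient. Whether that enrolment is a protocol deviation then depends on which section is read.

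The subject matter makes this more than an editorial slip. Sections 1.4.2.1 and 3.10.1 warn that acalabrutinib may further raise the risk of hemorrhage in patients on antiplatelet or anticoagulant drugs, and Section 1.4.2.1 reports fatal bleeds. Bleeding is an adverse event of special interest (Sections 4.1.3 and 6.1.5). The trial population is one that would normally not be treated.

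The CYP3A wording raises a similar question during treatment: is a patient who comes to need a strong inhibitor to stop study drug, or to continue under closer monitoring? Section 1.6.3.1 links CYP3A inhibition to a higher risk of tumor lysis during venetoclax titration.

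**Working it through.** No calculation applies: the point rests on no alpha, power, margin or event count. The check is a comparison of texts.

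**Step 1: antithrombotic drugs in use at screening, class by class**

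| Drug in use | Exclusion list (synopsis, 3.6.2) | Section 3.11.2 | Result |
|---|---|---|---|
| Vitamin K antagonist | Excluded by 8 and by 9 | Prohibited | Consistent |
| DOAC | Excluded by 9 (anticoagulant) | Includable | Contradiction |
| Acetylsalicylic acid | Excluded by 9 (platelet inhibitor) | Includable | Contradiction |
| NSAID | Not named; excluded only if classed as a platelet inhibitor | Includable | Depends on classification |
| Other platelet inhibitor | Excluded by 9 | Not named as includable | No conflict |

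**Step 2: can the two be read together?** One could take the Section 3.11.2 note to cover only drugs started after enrolment. Its words do not allow that: it speaks of patients already under treatment and says they can be included, which is a statement about entry. Nor does the note present itself as an exception to criterion 9, and criterion 9 does not refer to it. Criterion 8 adds to the doubt. It names vitamin K antagonists specifically, which is redundant if criterion 9 already bars every anticoagulant.

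**Step 3: strong CYP3A inhibitors.**
- At entry, criterion 8 excludes a patient who requires one. Section 3.12.2 allows enrolment if the drug can be stopped or replaced within 7 days before the first dose. These two are compatible.
- On treatment, Section 3.11.2 (list, table, closing sentence) and Appendix 3 prohibit them. Section 3.12.2 names strong inhibitors expressly and asks only for avoidance where feasible. A ban and a conditional recommendation are different rules.
- The monitoring sentence in Section 3.12.2 has no noun after CYP3A4. The sentence before it refers to inhibitors and inducers together. Read as inhibitor, it permits what Section 3.11.2 forbids. Read as inducer, it agrees with Section 3.11.2, which treats strong inducers as drugs to avoid where feasible.
- The stopping rule in Section 3.11.2 comes directly before a list running from chemotherapy to vitamin K antagonists. Strong CYP3A inhibitors are in a second list further down. The rule's reference to therapies listed below may or may not reach that second list.

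**Step 4: figures in the protocol that give context.** Section 1.4.2.1 gives grade 3 or higher bleeding in 2% of patients and any-grade bleeding in about 50%, the latter counting bruising and petechiae. Section 1.4.1 gives hemorrhage as 12%, with 1.5% at grade 3 or above. Section 3.12.2 gives about 5-fold acalabrutinib exposure with itraconazole. For venetoclax AUC it gives observed increases of 6.4-fold (ketoconazole) and 7.9-fold (ritonavir), and a predicted 5.8- to 7.8-fold for other strong inhibitors. The bleeding rates are overall rates on acalabrutinib, not the added risk from a DOAC or acetylsalicylic acid. None of these figures measures the effect of the contradiction.

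**The case against.** The best counter-argument is central control. Section 3.6.3 makes study office approval mandatory before randomization, and under Section 3.6.4 study physicians verify eligibility from the screening pages. This limits divergence between sites, and that part stands. It does not resolve the conflict, because the central reviewers apply the same two texts, and entry review does not govern drugs needed later.

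On strong CYP3A inhibitors, the ban is stated consistently in several places and only Section 3.12.2 departs from it. That also stands, and it is why this half is secondary.

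Several stronger readings are tempting, and the documents do not support them:

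- *That Section 3.11.2 readmits everyone barred by exclusion 9.* It names only DOACs, acetylsalicylic acid and NSAIDs.
- *That the protocol plainly orders both stopping and continuing for a patient who needs a strong CYP3A inhibitor.* The monitoring sentence is incomplete, and the reach of the stopping rule is uncertain. What is certain is a ban in one place against a softer recommendation in another.
- *That no protocol deviation can be defined.* For a patient who requires a strong CYP3A inhibitor at entry, criterion 8 is clear.
- *That the bleeding and exposure figures show the size of the harm.* They are background rates and interaction data. Section 3.10.1 also already calls for monitoring for bleeding in patients on these drugs.

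**Conclusion.** The eligibility contradiction is confirmed for DOACs and acetylsalicylic acid. It appears in both places where the exclusion list is printed, and no reading of the current text removes it. For NSAIDs it holds only on the assumption that they count as platelet inhibitors. It does not extend to vitamin K antagonists or to other platelet inhibitors.

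The CYP3A inconsistency is also real but narrower: a prohibition in Section 3.11.2 and Appendix 3 against a softer clause in Section 3.12.2, plus an unfinished sentence and a stopping rule of unclear scope.

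The number of patients affected cannot be derived, since the protocol gives no rate of use of these drugs. With 25 patients per arm, one patient is 1/25 = 4% of an arm; this only describes the arm size. Neither the sample size nor the 21% non-inferiority margin is affected. What is at stake is who is enrolled, how bleeding safety is handled, and whether the protocol is applied uniformly.

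**What to change.** 1. Reconcile exclusion 9 (synopsis and Section 3.6.2) with the note in Section 3.11.2, so that one eligibility rule covers DOACs, acetylsalicylic acid and NSAIDs. State whether NSAIDs count as platelet inhibitors for this purpose. Check that criteria 8 and 9 fit together on anticoagulants.
2. Reconcile Section 3.12.2 with Section 3.11.2 and Appendix 3 on strong CYP3A inhibitors. Complete the unfinished sentence so that it says inhibitor, inducer or both.
3. State in Section 3.11.2 whether the discontinuation rule covers the second list, and so strong CYP3A inhibitors.

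The sponsor's clinicians decide which rule applies in each case; this review takes no position on that. Section 7.1 requires amendments to be approved as appropriate before implementation, so sites should be notified through whichever route applies. The protocol does not give enrolment status. If patients have already been randomized, their antithrombotic and CYP3A medication should be checked against the settled rule.

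The cost is a few sentences of text and the approval step. No new procedure is needed, because Section 4.1.5 already records concomitant medication from 42 days before randomization to 2 years after the first dose.
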